1. SUMMARY

Although breast milk is recommended exclusively until 6 months of age, two-thirds of infants in the U.S. are fed infant formula. Despite an almost identical energy density between infant formula and breast milk, formula fed infants experience greater weight gain in the first year of life. We propose that unintentional overfeeding, of nearly one additional day of calories per week, due to the “over-scooping” of powdered formula contributes significantly to this phenomenon and potentially to the early development of childhood obesity, a significant public health problem. Research of US infants indicates that infant formula use is most prevalent in families with lower levels of education and poverty and as such infant formula is provided to families within the National Women, Infants and Children program. Given the higher prevalence of formula feeding in lower socioeconomic populations, there is an increased need for easy to follow instructions for formula preparation.

We recently completed the Baby Bottle Study at Pennington Biomedical (NCT01762631) which adapted the Remote Food Photography Method to estimate infant formula consumption in infants. An unexpected finding, despite following manufacturer infant formula preparation instructions, was that the weight of a single scoop of formula varied significantly. Ninety-five percent of the prepared scoops weighed more than the intended gram weight stated on the package. “Over-scooping” can result in increased caloric density and unintentional overfeeding of the infant. While the error for one scoop may have little impact on the overall nutrition of the infant, the error is compounded with every scoop and bottle fed over the course of a day.

In the proposed study we will assess the literacy and understanding of individuals to follow commercially available infant formula instructions. We will collaborate with the LA CaTS Health Literacy Core to improve the reading and comprehension of the manufacturer package instruction, and we will solicit the input of caregivers and key stakeholders to inform the development of educational intervention around infant feeding. Following modification of infant formula preparation instructions, we will conduct a randomized controlled trial that will test the efficacy of the modified instructions on infant overfeeding in comparison with the manufacturer package instructions. One hundred and fifty individuals will be asked to complete one study visit during which they will be asked to measure various serving sizes of infant formula following either the manufacturer package instructions or the modified instructions. The primary outcome variable will be powdered formula weight. We have designed qualitative and quantitative research studies to test the following specific aims.

1. **Aim 1 is to evaluate parental and caregiver literacy related to the use of commercially-available instructions for the preparation of infant formula.** *Hypothesis A: the health literacy of parents and caregivers to the instructions of commercially-available infant formula is variable. Hypothesis B: More than half of the parents and caregivers studied will not demonstrate adequate understanding of the infant formula instructions of the most commonly used infant formula in the US.*
2. **Aim 2 is to improve the accuracy and precision by which individuals’ measure powdered infant formula by increasing reading ease and clarity of preparation instructions.** *Hypothesis: Improving reading ease and adding explicit pictures that convey preparation instructions will increase the accuracy and precision of scoop weight when compared to the standard instructions given on the food label. We hypothesize that preparation instructions developed with a health literacy focus (Aim 1) will reduce the proportion of over-scooped bottles from 89% to 50%.*

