3.5.4. Focus Group Discussion

Focus group discussions will be led by a moderator who will follow a script of group discussion probes. During the focus group, participants will be asked to comment on discussion themes (e.g. attitudes towards infant feeding, current feeding practices, desired education regarding infant feeding, and recommendations to improve preparation instructions), and all responses will be audio and/or video tape-recorded and will be transcribed verbatim later. Responses will be de-identified in the transcript. Modified preparation instructions will be presented to the first focus group for discussion. The preparation instructions will be further modified based on participant feedback. Iterative focus groups will view and provide feedback on the preparation instructions modified by the previous focus group. Focus groups will continue until a satisfactory set of instructions are developed. Conducting focus groups in a stepwise fashion allow one focus group to build on the improvements recommended by another.

4. RESEARCH DESIGN: PHASE 2

Phase 2 is a randomized, controlled study to test the efficacy of the revised instructions on infant overfeeding in comparison with the instructions currently provided on the packaging (**Figure 4**). Individuals will be randomized in a 1:1 ratio to one of two groups:

1. **Group 1:** Group 1 participants will prepare infant formula following the standard infant formula preparation instructions provided by the manufacturer.
2. **Group 2:** Group 2 participants will prepare infant formula following the modified infant formula preparation instructions.

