6. DATA MANAGEMENT

6.1. Sample Size Consideration

In the Baby Bottle study, participants were asked to prepare a randomly ordered set of liquid baby formula (2, 4, 6, or 8 fl oz). Estimated proportions of participants over-scooping dry formula for bottles containing each amount were obtained from this preliminary data. A separate power analysis for the proposed study was carried out for each formula amount with the Baby Bottle estimates used to represent expected proportion of participants over-scooping dry formula when using the manufacturer preparation instructions. To ensure a well powered study, each estimate from the Baby Bottle data was reduced by an additional 15%. The most conservative results from the power analyses are presented in **Table 4** and provide a sufficient sample size to

achieve desired power when comparing the control and experimental group proportions of over-scooping for any individual formula amount as well as across all amounts. In the proposed study, we hope to see the proportion of participants over-scooping formula reduced to 50% following use of the new preparation instructions. 75 participants will be enrolled in each study group, ensuring 80% power to detect this decrease.

Table 4. Sample size calculations¹

Power (%)	Proportion over-scooped: OLD	Proportion over-scooped: NEW	N Per Group
80	0.8	0.7	294
80	0.8	0.6	82
80	0.8	0.5	39
80	0.8	0.4	23

¹*Old Proportion* represents the proportion of participants expected to over-scoop formula when using the existing instructions. *New Proportion* represents the reduced proportion of participants that are expected to over-scoop formula when using the new instructions.

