6.3. Data Analysis Plan

To address the primary aim, dry formula weights will be compared to package recommendations (i.e. 8.7 g per scoop) and classified as under-scooped, accurate scoop, or over-scooped. The proportion of bottles that are over-scooped will be compared between the two groups. Both univariate and multivariate analyses will be employed. 2x2 contingency tables with counts of participants over-scooping in each treatment arm will be constructed and chi-square tests used to compare raw proportions. This will be carried out separately for each bottle size. In addition, estimated probabilities of over-scooping for each group will be obtained from logistic regression models allowing for adjustments for bottle size and any other chosen covariates. Group-level odds ratios constructed from the estimated probabilities will be compared using two-sample t-tests. For all tests, statistical significance is defined as $p < \alpha$. Adjustments for multiple comparisons will be made when appropriate.

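### Powder weight is declared the primary outcome, but only the over-scooped proportion is powered and compared, so no between-arm estimate of powder weight or percent excess is planned

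*Combined protocol and SAP*

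**What the plan says.** - **Declared outcome.** The Summary says "The primary outcome variable will be powdered formula weight". This is a continuous quantity.
- **Aim 2 (Summary).** The hypothesis has two parts. The first is that clearer instructions "will increase the accuracy and precision of scoop weight when compared to the standard instructions given on the food label". The second, the only one with numbers, is that they "will reduce the proportion of over-scooped bottles from 89% to 50" per cent.
- **Purpose of Phase 2 (section 4).** The trial is to "test the efficacy of the revised instructions on infant overfeeding in comparison with the instructions currently provided on the packaging".
- **Data (4.5.3).** Each participant prepares 8 bottles, two at each of four sizes. Dry powder weight is recorded to 0.1 g.
- **Sample size (6.1).** The calculation is meant to "achieve desired power when comparing the control and experimental group proportions of over-scooping for any individual formula amount as well as across all amounts". The target is binary: "we hope to see the proportion of participants over-scooping formula reduced to 50% following use of the new preparation instructions". It concludes: "75 participants will be enrolled in each study group, ensuring 80% power to detect this decrease".
- **Analysis (6.3).** For the primary aim, each dry weight is set against 8.7 g per scoop and coded as under, accurate or over. Then "The proportion of bottles that are over-scooped will be compared between the two groups", by chi-square tests for each bottle size and by logistic regression. The univariate and multivariate analyses that 6.3 mentions are spelled out only as these two.

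**The concern.** The variable called primary has no between-arm estimate, model or power statement. The quantity that is tested is a recoding of it, and the recoding discards the amount of powder.

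Amount is what the rationale rests on. Section 2.3 reports an average excess of 11%, turns it into 22 kcal/fl oz, and in Table 1 into 39 to 65 kcal/day. A proportion above label cannot be turned into grams or calories. Under-filling is merged with accurate filling as not over-scooped, so an arm that drifted into under-filling would look successful although accuracy had not improved. A reader of the results also could not tell from the plan whether weight or the proportion decides the trial.

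**Working it through.** **1. What the sample size rests on.** Inputs from Table 4: old proportion 0.8; new 0.7, 0.6, 0.5 or 0.4; power 80%. No numerical alpha is given, so two-sided 0.05 is assumed. The formula is

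n = [1.96·√(2p̄(1−p̄)) + 0.842·√(p1(1−p1) + p2(1−p2))]² / (p1−p2)², with p̄ = (p1+p2)/2.

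It gives 294, 82, 39 and 23 per group, matching all four rows. The sample size is therefore wholly a two-proportion calculation. At the 75 per group to be enrolled, power is 97.7% for 0.8 versus 0.5, and above 99.9% for 0.89 versus 0.5. Neither figure is power for a weight difference.

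**2. What the recoding discards.** Take a one-scoop portion, label 8.7 g, and the range in section 2.3 (−24% to +140%):

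| Dry weight | Deviation | Counted as |
|---|---|---|
| 8.8 g | 0.1/8.7 = +1.1% | over-scooped |
| 8.7 × 2.40 = 20.9 g | +140% | over-scooped |
| 8.7 × 0.76 = 6.6 g | −24% | not over-scooped |

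Section 6.3 gives no tolerance for an accurate scoop. With a tolerance, the first row would move to just beyond that band and the point would be unchanged.

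**3. What the rationale needs.** Table 1 multiplies energy intake by the excess: 0.11 × 350 = 38.5 (shown as 39) and 0.11 × 590 = 64.9 (shown as 65) kcal/day. If the excess were halved to 5.5%, the figures would be 0.055 × 350 = 19 and 0.055 × 590 = 32 kcal/day, assuming correct water. Detecting such a change requires an estimate of mean percent excess in each arm, and none is planned.

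**4. Does weight or the proportion have more power?** Assume 75 per arm, two-sided 0.05, one value per participant and a control mean of +11%. The documents give no SD.

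*Normal errors*, with over-scooped proportion Φ(mean/SD). The first three SDs are those implied by mean 11 and 95.4% (607/636), 89% or 80% over label. The last takes the ±0.6 in section 2.3 as a standard error over 636 bottles: 0.6 × √636 = 15.1.

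| SD (points) | Excess falls to | Proportions | Power, proportion | Power, weight |
|---|---|---|---|---|
| 6.5 | 5.5% | 0.955 vs 0.801 | 83% | >99% |
| 9.0 | 5.5% | 0.890 vs 0.730 | 71% | 96% |
| 13.1 | 5.5% | 0.799 vs 0.663 | 47% | 72% |
| 6.5 | 8% | 0.955 vs 0.891 | 31% | 80% |
| 15.1 | 5.5% | 0.766 vs 0.642 | 39% | 60% |

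These SDs fit the reported maximum poorly: +140% lies (140 − 11)/6.5 ≈ 20 SDs above the mean at SD 6.5, and about 10 at SD 13.1.

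*Right-skewed errors*: excess = −1.76 + 8.23·exp(0.937·Z), Z standard normal. This has mean 11, SD 15.1 and 95% above zero. By simulation:

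| Effect | Power, proportion | Power, weight |
|---|---|---|
| Every value 5.5 points lower | about 100% | about 65% |
| Every value 3 points lower | about 98% | about 27% |
| Every value halved | about 5% | about 87% |

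Halving leaves the sign of each value unchanged, so the proportion over label stays at 95% in both arms and the binary test rejects only at its error rate. This model cannot reach the reported −24%, so it too is only illustrative. The ranking reverses with the form of the effect.

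**5. What the added estimate could deliver.** If ±0.6 is a standard error over 636 bottles, SD = 15.1; if over 53 participants, SD = 0.6 × √53 = 4.4. With 75 per arm, the 95% CI half-width is 1.96 × SD × √(2/75), or 4.8 and 1.4 points. The difference detectable with 80% power is (1.96 + 0.842) × SD × √(2/75), or 6.9 and 2.0 points, against a baseline excess of 11.

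**The case against.** The strongest reply is that the documents can be read coherently: weight is what is measured, and over-scooping relative to label is how it is analysed. The only numerical hypothesis is the fall from 89% to 50%, and 6.1 and 6.3 both follow it. This stands as a reason to let the proportion remain primary. It does not supply a between-arm estimate of the variable that the Summary names, nor of the accuracy that Aim 2 promises.

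Three stronger readings are tempting, and the documents do not support them:

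- *The trial could not say how far overfeeding fell.* Every dry weight is recorded to 0.1 g, so the answer can be computed. What is missing is its pre-specification.
- *Comparing weights would have more power.* This holds in the normal-error cases above and fails under a right-skewed model with a uniform shift.
- *The proportion should be demoted because its test is weak.* At the plan's own target it has about 98% power. Demotion would replace the one hypothesised and powered outcome with one that has no SD or target difference in the documents.

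It is also fair to object that a mean signed deviation lets over- and under-filled bottles cancel and says nothing about precision, and that section 2.2 recognises water as a second source of energy-density error. The first is why absolute deviation belongs beside it. The second limits any conversion to calories to an assumption of correct water.

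**Conclusion.** The point holds as a mismatch between the declared outcome and the analysis, and as a gap in pre-specification. The Summary names powder weight; 6.1 and 6.3 power and compare only the proportion over-scooped. No between-arm difference in weight or percent excess is planned, so the quantity behind the 11% and 39–65 kcal/day rationale would go untested. This rests on the text alone and needs no assumed SD.

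The size of any power gain or loss cannot be fixed from the documents. The illustrations assume two-sided 0.05, one value per participant and a chosen error model, and they point both ways. They show only that the proportion and the mean excess can move separately, so neither can stand in for the other. The change should be made, but it does not call the planned sample size into question for the binary comparison.

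**What to change.** 1. Make the Summary, 6.1 and 6.3 name the same primary outcome. The over-scooped proportion may stay primary, since it is the outcome hypothesised and powered; the Summary sentence would then describe powder weight as the measurement from which it is derived.
2. Add to 6.3 a pre-specified comparison. For each participant, average the signed percent deviation of dry powder weight from label over the 8 bottles. Report the between-arm difference in means with a 95% CI, overall and by bottle size. One value per participant also deals with the repeated bottles in the overall comparison.
3. Report mean absolute percent deviation in the same way, so that over- and under-scooping do not cancel.
4. Because the preliminary range suggests right skew, add a robust or rank-based sensitivity analysis.
5. Make no claim that the weight comparison is generally more powerful. If expected precision is stated, give it as a range with its SD assumption.

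The cost is SAP wording and a little more analysis. No new data, visits or participants are needed. If weight were made primary instead, 6.1 would need its own SD and target difference, which the documents do not contain.

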2. BACKGROUND AND SIGNIFICANCE

2.1. Significance

The 1,000 days between a woman's pregnancy and the child's second birthday is a critical period for growth and development. During this time the child is particularly vulnerable to the environment and permanent metabolic and developmental changes that may occur. Inadequate nutrition and improper feeding practices early in life leads to childhood obesity and chronic diseases in adulthood such as obesity, diabetes, and cardiovascular disease [1] and therefore, the National Institutes of Health is currently soliciting proposals to understand the development of obesity in children within this critical window for metabolic programming (PAR-14-323). From the outset, the introduction of synthetic infant formula as an alternative to breast milk was met with tremendous scrutiny [2]. While improvements to the composition of synthetic infant formula have been made since its development in 1865 including fortification with iron and omega-3 fatty acids [2] and despite an almost identical energy density between formula and breast milk, formula fed infants experience greater weight gain in the first year of life than exclusively breastfed infants [3]. Potential mechanisms linking infant formula feeding and childhood adiposity include lower levels of feeding self-regulation and increased appetite due to differences in sucking biomechanics between the bottle and breast [4-6], differences in established feeding practices [7], and maternal attitudes towards infant feeding.

Despite the benefits of breastfeeding and the recommendation of the World Health Organization and the American Academy of Pediatrics for exclusive breastfeeding until six months of life [8], over 80% of infants in the United States receive infant formula prior to their six month birthday [9, 10]. Given that the majority of infants in the U.S. receive infant formula in the first year of life, it is perplexing that there is little to no current NIH funding dedicated to better understanding the link between infant formula and obesity development in young children. On the other hand, there is an abundance of research that focuses on the promotion of breastfeeding or mechanistic studies to understand why breast milk may be protective against childhood obesity which seems counterintuitive. We agree that research on breastfeeding and breast milk is important however the scientific community is neglecting the equally or arguably more important research of infant feeding in general and in particular feeding with infant formula. If this trend research continues, the childhood obesity epidemic will likely only be worsened because many of barriers to breastfeeding in the US, as pointed out in the US Surgeon General Report in 2011 [11], including maternal obesity, lack of social and family support and unpaid maternity leave are not likely to be overcome in the near future. Furthermore, evaluating the health literacy and comprehension of infant formula instructions is critical because the USDA's Special Supplemental Nutrition Program for Women, Infants, and Children (WIC) is the largest purchaser of infant formula making WIC recipients the largest consumer of infant formula in the United States [12]. Individuals who receive WIC benefits are generally from racial and ethnic minority groups, GED certificate recipients or individuals below the 12th grade education level [13], and these demographics are consistent with a population with low health literacy [14]. Infant formula preparation instructions must therefore be written and designed to accommodate a low level of health literacy to ease readability, improve caregiver competency, and increase preparation accuracy to ensure proper feeding of the nearly 662,000 formula fed infants receiving WIC services per year. Thereby, research examining the health literacy of individuals in the understanding of infant feeding and in particular in the preparation of infant formula are critical to evaluate. Moreover interventions for caregivers that focus on infant feeding in general and infant formula in addition to breastfeeding in both the pre- and post-natal periods need to be developed and tested to address this major public health issue.

2.2. Innovation

Through this highly innovative project we will, for the first time, conduct qualitative research to evaluate the health literacy of infant formula instructions. In collaboration with the LA CaTS Health Literacy Core, we aim to improve the reading and comprehension of package preparation instructions. The revised infant formula

preparation instructions will be further modified through the recommendations of repeated focus groups. Lastly, we test the efficacy of the new instructions on infant overfeeding by asking volunteers to measure infant formula using the standard preparation instruction or the revised instructions in a randomized controlled trial. This is a novel translational study which will demonstrate that toolkits aimed to educate caregivers in the proper preparation of infant formula along with improved preparation instructions need to be developed. With easier to follow preparation instructions, caregivers will less likely overfeed infants resulting in decrease infant adiposity and risk for childhood obesity.

[figure not shown]
Our study is highly novel because: 1) it addresses infant formula feeding which is postulated to be a major factor in the development of childhood obesity which is a major public health concern, 2) we have highly provocative preliminary data from a recently completed study at Pennington Biomedical Research Center (PBRC) that shows adults including caregivers of infants grossly overestimate infant formula which would lead to a significant overfeeding, 3) we plan for the first time to carryout qualitative research that assesses the literacy and understanding of individuals to follow commercially available infant formula instructions and 4) we will solicit the input of caregivers and key stakeholders to inform the development of educational intervention around infant feeding. The results of our study therefore translate our previous research findings to improve the understanding of infant feeding and in particular the accuracy of infant formula preparation to prevent unintentional overfeeding and to inform public health strategies related to the prevention of obesity from birth.

The majority of the commercially available infant formula exists in powdered form. Caregivers are required to correctly interpret the package label to accurately estimate the serving size and prepare a bottle of formula for the infant. This is particularly problematic because adults are unable to accurately measure estimate portion sizes [8, 15] and the preparation of infant formula requires an accurate estimate of not one but two parts that can impact the energy density of the meal; the powdered infant formula and the added water. Despite strict governance by the FDA on the precise formulation of infant formula [9], it is surprising that there is no consistency between products in the preparation instructions provided to consumers on the label and the measuring scoop used to prepare the required serving size. Difficulty in understanding preparation instructions together with an inaccurate estimation of portion sizes would lead to an incorrect preparation of infant formula bottle.

